4.17 Handling of Dropouts or Missing Data

No imputation of missing data will be performed except for partial dates imputation mention in Section 6.2.

4.18 Subgroup Analysis

Not Applicable

4.19 Planned Interim Analyses

Not Applicable

4.20 Determination of Sample Size

No formal sample size calculations were performed. Thirty-two patients were chosen based on feasibility and are considered sufficient to meet the study objectives of this exploratory study.

4.21 Changes in the Conduct of the Study or Planned Analysis

Exploratory population definition is more elaborately defined as per study need.

6 APPENDICES

6.1 Schedule of Assessments

Table 6-1 Schedule of Assessments

Evaluation	Screening visit Treatment period					Follow-up/ End of treatment	Early termination procedures		
	Days								
	-28 to -2	-1	1	2-7	8, 9	10	14		
Informed consent	Х								
Admission		Х							
In-house stay		Х	Х	Х	Х	Х			
Ambulatory visits	X						Х	Х	
Discharge						Х			
Inclusion/exclusion criteria	X	Х	Х						
Medical history	X	Х							
Disease activity data (ACR20/50/70, DAS28, CDAI, SDAI)			X ¹	X ²					
Blood sampling for ESR, assessed as part of disease activity data			X ¹	X ²					
Demographics	Х								
Weight and height (height only at Screening)	Х	Х				Х			
Viral serology (HBsAG, anti- HBc, anti-HCV, anti-HIV)	X								
Drug, alcohol, and cotinine screen	X	Х							
SARS-CoV-2 real time RT-PCR	X	Х							
IGRA-TB test (Quantiferon)	Х								
Chest X-ray	Х								
Randomization			Х						
Study drug administration			Х	Х					
Urine pregnancy test (females)	Х	X					Х	X	
FSH (post-menopausal females)	X								
Physical examination ³	Х	Х				Х	Х	Х	

CONFIDENTIALProject Document Version No. 2.0Project Document Effective Date: Date of last signature

Evaluation	Screening visit Treatment period						Follow-up/ End of treatment	Early termination procedures	
		Days							
	-28 to -2	-1	1	2-7	8, 9	10	14		
Clinical laboratory tests (clinical chemistry, hematology, coagulation, and urinalysis)	X	X	X ¹	X ⁴	X	X	Х	Х	
Vital signs	Х	Х	X ⁵	Х	Х	Х	Х	Х	
12-lead ECG ⁶	X ⁶	X ⁷	X ⁸	X ⁸	Х	Х	Х	Х	
Telemetry			X9	X9					
PK blood sampling ¹⁰			Х	Х	Х	Х			
PK urine collection ¹¹			Х	Х	Х	Х			
Biomarker blood sampling			\mathbf{X}^1	X^2					
Blood sampling for possible future pharmacogenetic assessments		X ¹²							
Blood sampling for possible future metabolite assessments ¹⁰			X	X	X	Х			
Blood sampling for possible future PD assessments			X ¹	X ²					
Prior/concomitant medications	X	X	X	X	X	X	X	X	
AE monitoring ¹³	X	Х	X	Х	Х	Х	Х	Х	

ACR = American College of Rheumatology; AE = adverse event; CDAI = clinical disease activity index; DAS28 = disease activity score 28; ECG = electrocardiogram; ESR = erythrocyte sedimentation rate; FSH = follicle stimulating hormone; HBc = hepatitis B core; HBsAG = hepatitis B surface antigen; HCV = hepatitis C virus; HIV = human immunodeficiency virus; ICF = informed consent form; IGRA-TB = interferon gamma release assay for tuberculosis; PD = pharmacodynamic; PK = pharmacokinetics; RT-PCR = reverse transcription polymerase chain reaction; SARS-CoV-2 = severe acute respiratory syndrome coronavirus 2; SDAI = simplified disease activity index.

- 1. Disease activity data (ACR20/50/70, DAS28, CDAI, SDAI, and blood sampling for ESR), blood for clinical laboratory tests, blood for biomarker assessments, and blood for possible future PD assessments will be collected prior to dosing on Day 1. Blood sampling for ESR will be collected and assessed at local laboratory.
- 2. Disease activity data (ACR20/50/70, DAS28, CDAI, SDAI, and blood sampling for ESR), blood for biomarker assessments, and blood for possible future PD assessments will be collected on Day 7 only. Blood sampling for ESR will be collected and assessed at local laboratory.
- 3. A full physical examination will be performed at the Screening Visit, Day 14, and Early termination visit; a brief physical will be performed on Days -1 and 10.
- 4. Blood for clinical laboratory tests will be withdrawn once on Days 4 and 7.
- 5. Vital signs will be collected at pre-dose and 1, 2, 4, 8, and 12 hours after dosing on Day 1.
- 6. 12-lead ECG will be conducted before blood sampling.
- 7. 12-lead ECG will be repeated once for eligibility confirmation at Screening and Day -1.

CONFIDENTIAL

- 8. 12-lead ECG will be recorded at baseline and at 1, 2, 4, and 8 hours after dosing on Days 1 and 7.
- 9. Starting 2 hours prior to dosing and until 12 hours after dosing on Days 1 and 7.
- 10. Blood for PK sample analysis to determine parent and its metabolite concentrations and for possible future metabolite assessments will be sampled at pre-dose and 0.25, 0.5, 1, 1.5, 2, 3, 4, 6, 8, 12, 16, and 24 hours (pre-dose of Day 2) after dosing on Day 1, pre-dose on Days 3, 4, 5, 6, and on 7, at pre-dose and 0.25, 0.5, 1, 1.5, 2, 3, 4, 6, 8, 12, 16, 24, 48, and 72 hours after dosing on Day 7 (the sampling time points may be adjusted based on the PK results obtained from the previous parts or cohorts). The last dose will be administered on Day 7.
- 11. Urine for PK sample analysis will be collected at 0 (pre-dose) to 6, 6 to 12, and 12 to 24 hours after dosing on Day 1, and from 0 (pre-dose) to 6, 6 to 12, 12 to 24, 24 to 48, and 48 to 72 hours after dosing on Day 7. Urine collection intervals may be adjusted based on the PK results obtained from the previous parts or cohorts, e.g., if plasma PK sampling times are adjusted, the urine sampling times will be updated.
- 12. Sample will be obtained only from patients that consent to pharmacogenomics sampling.
- 13. Any AEs occurring after the patient signs the ICF will be collected and monitored throughout the study via safety assessments, observation, and patient reporting.

6.2 Imputation Rules for Partial Dates

Imputed dates and time will NOT be presented in the listings.

Table 6-2 and Table 6-3 present algorithm for imputing partial dates for TEAE and prior/concomitant medication respectively.

Table 6-2 Algorithm for Treatment-Emergent Adverse Events:

Start/Increase Severity Date	Stop Date	Action
Known	Known	Considered as a treatment-emergent adverse event
		(TEAE) if start date on or after the date of the first dose
		of investigational product (IP)
	Partial	Considered as a TEAE if start date on or after the date
		of the first dose of IP. The last day of the month and the
		last month (ie, December) will be used if the stop
		day/month is missing.
	Missing	Considered as a TEAE if start date on or after the date
		of the first dose of IP
Partial, but known components show	Known	Not a TEAE. The first day of the month and January
that it cannot be on or after first IP taken		will be used if the start day/month is missing.
date		
	Partial	Not a TEAE. The first day of the month and January
		will be used if the start day/month is missing. The last
		day of the month and the last month (ie, December) will
		be used if the stop day/month is missing.
	Missing	Not a TEAE. The first day of the month and January
		will be used if the start day/month is missing.
Partial, could be on or after first IP taken	Known	Considered as TEAE, if stop date is after first IP taken
date		date. The first IP taken date will be used if start date is
		in the same month/year with first IP taken date, or the
		first day of the month and January will be used if the
		start day/month is after first IP taken date
		Considered as not TEAE, if stop date is prior to first IP
		taken date. The first day of the month and January will
		be used if the start day/month is missing.
	Partial	Considered as TEAE. The first IP taken date will be
		used if start date is in the same month/year with first IP
		taken date, or the first day of the month and January will
		be used if the start day/month is after first IP taken date.
		The last day of the month and the last month (ie,
		December) will be used if the stop day/month is
		missing.
	Missing	Considered as TEAE. The first IP taken date will be
		used if start date is in the same month/year with first IP
		taken date, or the first day of the month and January will
		be used if the start day/month is after first IP taken date.
Missing	Known	Considered as TEAE if stop date is on or after the date
		of the first dose of IP.
	Partial	The last day of the month and the last month (ie,

Start/Increase Severity Date	Stop Date	Action
		December) will be used if the stop day/month is missing. If the imputed stop date is on or after the first dose of IP considered as a TEAE; if the year is missing, considered as a TEAE
	Missing	Considered as a TEAE

Table 6-3 Algorithm for Prior/Concomitant Medications Categorization:

Start Date	Stop Date	Action
Known	Known	If stop date is prior to the date for the first dose of IP, considered as prior; if stop date is on or after the date for the first dose of IP, considered as concomitant.
	Partial	The last day of the month and the last month (ie, December) will be used if the day/month of stop date is missing. If the impuated stop date is prior to the date for the first dose of IP, considered as prior; if the imputed stop date is on or after the date for the first dose of IP, considered as concomitant.
	Missing	Considered as concomitant.
Partial	Known	If stop date is prior to the date for the first dose of IP, considered as prior; If stop date is on or after the date for the first dose of IP, considered as concomitant. The first day of the month and January will be used if the start day/month is
		missing.
	Partial	The last day of the month and the last month (ie, December) will be used if the day/month of stop date is missing. If the impuated stop date is prior to the date for the first dose of IP, considered as prior; if the imputed stop date is on or after the date for the first dose of IP, considered as concomitant. The first day of the month and January will be used if the start day/month is missing.
	Missing	Considered as concomitant. The first day of the month and January will be used if the start day/month is missing.
	•	•
Missing	Known	If stop date is prior to the date for the first dose of IP, considered as prior; if stop date is on or after the date for the first dose of IP, considered as concomitant.
	Partial	The last day of the month and the last month (ie, December) will be used if the day/month of stop date is missing. If the impuated stop date is prior to the date for the first dose of IP, considered as prior; if he imputed stop date is on or after the date for the first dose of IP, considered as concomitant.
	Missing	Considered as concomitant.

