6.4 Study Intervention Compliance

When patients are dosed at the site, they will receive study intervention directly from the Investigator or designee, under medical supervision. The date and time of each dose administered in the clinic will be recorded in the source documents. The dose of study intervention and study patient identification will be confirmed at the time of dosing by a member of the study site staff other than the person administering the study intervention.

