4.8 Treatment Exposure and Compliance

4.8.1 Treatment Exposure

A by-patient listing of patient exposure to study drug will be generated. The listing will include date and time of administration.

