4.13.1 Adverse Events

All outputs for AEs/treatment-emergent adverse events (TEAEs) will be based on the SAF unless specified separately in TLF shells. AEs are to be classified by using Medical Dictionary for Regulatory Activities (MedDRA®), Version 25.0 or higher and assigned to a System Organ Class (SOC) and Preferred Term (PT).

All AE will be summarized by MedDRA terms and treatment groups. It will include evaluation of the number of AEs and the number and percentage of patients reporting at least one AEs.

Summaries of AEs will include the following:

- Incidence of AEs Overview (by cohort/treatment and overall)
- Incidence of TEAEs (by cohort/treatment and overall, SOC, and PT)
- Incidence of TEAEs by relationship (by cohort/treatment and overall, SOC, and PT)
- Incidence of TEAEs by maximum severity (mild/moderate/severe, by cohort/treatment and overall, SOC, and PT)
- Incidence of TEAEs leading to discontinuation of study treatment
- Incidence of SAEs
- Incidence of TEAEs Related to IMP by maximum severity (mild/moderate/severe, by cohort/treatment and overall, SOC, and PT)

Summary tables will contain counts of patients, percentages of patients in parentheses, and the number of events where applicable. A patient who has multiple events in the same SOC and PT will be counted only once in the patient counts, but all events will be included.

All Adverse Events (AEs)

Adverse events will be individually listed per patient number, presenting assigned treatment, verbatim term, Primary SOC, PT, treatment emergence (yes or no), date and time of onset, date and time of last study drug administration before AE, time from onset since last study drug administration, severity and seriousness, relationship to study drug, the required action taken, outcome, if it is a reason for drop out, and if it is AESI or not.

Treatment-emergent Adverse Event

A TEAE will be defined as any AE that emerge during treatment (i.e., AE which started after study drug administration or pre-existed that worsened in severity after study drug administration) and those will be analyzed for the purpose of safety analysis.

TEAEs will be summarized by SOC and PT, including the number and percentage of patients experiencing events, separately.

Severity

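### SAP Table 6-2 classes Day 1 pre-dose adverse events as treatment-emergent by calendar date, while SAP 4.13.1 requires onset or worsening after dosing

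*SAP*

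**What the plan says.** SAP 4.13.1 (Adverse Events) gives the definition in words. A TEAE is an "AE which started after study drug administration or pre-existed that worsened in severity after study drug administration". The reference point is the administration, not the day on which it happens.

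SAP 6.2, Table 6-2, gives an algorithm. Its first column covers the date of onset or of increase in severity. Where that date is known, the event is a "TEAE) if start date on or after the date of the first dose". This criterion appears in three rows, for a stop date that is known, partial or missing. None of them mentions time of day.

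The section introduces its tables as follows: "Table 6-2 and Table 6-3 present algorithm for imputing partial dates for TEAE and prior/concomitant medication respectively".

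The plan provides for the times that the 4.13.1 definition needs:

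- The adverse event listing in SAP 4.13.1 carries "date and time of onset, date and time of last study drug administration before AE".
- For exposure, SAP 4.8.1 states: "The listing will include date and time of administration".
- Protocol 6.4 states: "The date and time of each dose administered in the clinic will be recorded in the source documents".

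The Day 1 pre-dose period is also under observation. A footnote to the SAP 6.1 schedule reads "Any AEs occurring after the patient signs the ICF will be collected and monitored throughout the study", and the telemetry footnote reads "Starting 2 hours prior to dosing and until 12 hours after dosing on Days 1 and 7".

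**The concern.** One SAP gives two classification rules for the same record, and they disagree for a patient who has an event on the morning of Day 1 before taking the tablet. Patients are in-house from Day -1. Before the first dose they have telemetry, vital signs, an ECG and blood sampling, so an event with a known pre-dose time is possible.

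If Table 6-2 is programmed as written, an event known to precede any drug enters the TEAE tables. Two further effects follow from the SAP's own rules:

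- SAP 4.13.1 counts a TEAE with missing relationship as related to the last study drug given. A Day 1 pre-dose event has no earlier dose, yet it could enter the related-TEAE summary.
- SAP 4.2.4 takes the last value before first dose as baseline, and SAP 4.13.3 says that clinically significant laboratory abnormalities are recorded as adverse events. A finding dated to the Day 1 pre-dose sample could be baseline in the laboratory tables and treatment-emergent in the adverse event tables.

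Adverse event incidence and severity is one of the primary safety endpoints, and it is read by dose in groups of six.

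**Working it through.** The plan states no figure to reproduce. The check has two parts: apply both rules to the same onset times, then size the effect of one changed classification.

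**Rules**

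- Table 6-2, known start: TEAE if date(onset or worsening) ≥ date(first dose).
- SAP 4.13.1: TEAE if date-time(onset or worsening) > date-time(first dose).

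**Test cases.** The documents say only that dosing is in the morning. A Day 1 dose at 08:00 is assumed for illustration.

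| Onset | Table 6-2 | SAP 4.13.1 |
|---|---|---|
| Day -1, 20:00 | not TEAE | not TEAE |
| Day 1, 06:30 (pre-dose, inside the telemetry window) | TEAE | not TEAE |
| Day 1, 07:45 (pre-dose) | TEAE | not TEAE |
| Day 1, 09:00 (post-dose) | TEAE | TEAE |
| Day 2 | TEAE | TEAE |

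The rules part only between midnight and the dose on the first-dose date. The assumed hour moves the end of that interval but not the finding. The same comparison applies to a pre-existing event that worsens in that interval.

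**Size**

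- SAP 4.2.1 gives 6 active patients per cohort and 2 on placebo in each of 4 cohorts. SAP 4.13 pools placebo, so its denominator is 4 × 2 = 8.
- SAP 4.2.6 uses N as the denominator. If k of n patients have a TEAE, one added patient shifts incidence by (k + 1)/n − k/n = 1/n.
- Active cohort: 1/6 = 16.7 percentage points.
- Pooled placebo: 1/8 = 12.5 percentage points.
- Overall column, all 32 patients: 1/32 = 3.1 percentage points.

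These shifts require that the pre-dose event is the patient's only TEAE. If the patient has another, overall incidence does not change. A system organ class or preferred term row shifts by 1/n if the event is the patient's only TEAE in that row. The documents give no expected number of such events, so no expected shift can be calculated.

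**The case against.** The best defence is that section 6.2 is about partial dates, that SAP 4.17 refers to it only for imputing them, and that 4.13.1 therefore governs complete dates. This does not settle the matter. The rows at issue are for known start dates, and in the known-stop row nothing is imputed at all. They state a classification rule, and nothing in the SAP gives 4.13.1 precedence. What does stand is that the documents do not show which rule will be programmed: the table shells and programming specifications are not part of them. A reader might infer that pre-dose events will certainly be counted. The documents support only that one of the two written rules counts them.

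Several limits also stand. The table can only over-count, it treats active and placebo alike, and it hides no event. The listing shows onset time and last dose before the event, so a careful reader could find the case. Eligibility is still checked on Day 1, so some patients with notable pre-dose findings may never be dosed or enter the safety population. Under protocol 10.3.1, signs of the studied disease are not adverse events unless more severe than expected, so the Day 1 joint assessment is a weak source.

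Two stronger readings are not supported:

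- **TEAE incidence is the primary outcome.** The primary endpoints are a set that also includes vital signs, ECG and telemetry, laboratory abnormalities, events of special interest and physical examination. They name adverse event incidence and severity, not TEAE incidence. No hypothesis is tested.
- **The tables would contradict the treatment-emergence flag in the listing.** The SAP gives no separate derivation for that flag. It may come from the same rule as the tables.

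**Conclusion.** The inconsistency holds in a narrow form. For a known start or worsening date equal to the first-dose date, Table 6-2 makes a pre-dose event a TEAE and SAP 4.13.1 does not, with no stated order of precedence. Events on any other date, and post-dose events on Day 1, are classified alike.

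The conclusion rests on the text of the two sections and on onset and dose times being recorded as planned. A reader might take the shifts of 16.7 and 12.5 points as the expected distortion. They are the effect of one patient under the sole-TEAE condition, and the number of such patients is probably small. The correction is still worth making: the table departs from the SAP's own definition, groups of six are sensitive to a single patient, and the information needed is already planned for collection.

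**What to change.** In all three known-start rows of Table 6-2 (stop date known, partial or missing), add a tie-break for a start or worsening date equal to the first-dose date:

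1. If the time is known, compare it with the time of first dose. Class the event as a TEAE only if it started or worsened after dosing, as in SAP 4.13.1.
2. If the time is missing, keep the present date-only rule, so that the event counts as a TEAE.

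Write the tie-break for worsening as well as onset, since the column covers both. One sentence in 4.13.1 should say that the date-time comparison governs whenever both times are known.

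The cost is an edit to three table rows, one sentence, and the matching line of derivation code. No new data are needed. SAP section 1 already provides a Statistical Method Modification Form for changes after finalization.

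### SAP Table 6-2, partial start date that could fall on or after first dose: a partial stop date is never tested, so an AE that ended before dosing can be classed a TEAE, and a known stop on the first-dose date gets no class

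*SAP*

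**What the plan says.** The rows at issue in SAP Table 6-2 are those whose start-date category is "Partial, could be on or after first IP taken" date.

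- **Stop date known.** Two branches: "Considered as TEAE, if stop date is after first IP taken" date, and "Considered as not TEAE, if stop date is prior to first IP" date. Each carries its own imputation rule for the start date.
- **Stop date partial.** One unconditional class: "Considered as TEAE. The first IP taken date will be" used as the start under certain conditions. The cell also imputes the stop to the end of the month or year, but compares it with nothing.

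The rows for a wholly missing start date work differently. With a known stop: "Considered as TEAE if stop date is on or after the date" of first dose. With a partial stop: "If the imputed stop date is on or after the first dose of IP considered as a TEAE", and a stop with no year also gives a TEAE.

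Table 6-3, for medications, follows the second pattern: "if the imputed stop date is on or after the date for the first dose of IP, considered as concomitant".

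SAP Section 4.13.1 defines a TEAE as an "AE which started after study drug administration or pre-existed that worsened in severity after study drug administration". Section 4.17 allows no imputation of missing data other than the partial-date rules of Section 6.2.

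**The concern.** Treatment emergence decides which events enter the TEAE tables by system organ class and preferred term, severity and relationship. Safety and tolerability are the primary objective, so the rule for this flag should give one answer for every combination of dates, and that answer should agree with the definition in Section 4.13.1.

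Pre-dose events will be in the database. AEs are collected from signature of the consent form (Protocol Section 8.4.1; SAP Table 6-1, footnote 13), and screening starts up to Day -28. A rule that ignores the stop date can therefore attribute to a dose group an event that was over before any dose was given. A rule with no branch for a stop on the first-dose date leaves that choice to the programmer. The table is also inconsistent with itself: an AE with some start information can be classed less accurately than the same AE with none.

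**Working it through.** The plan states no figure on this point, so the check applies the table to test dates. The first dose is set at 5 June 2023. That date is an illustration and does not come from the documents.

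**Known stop.** The cell's two conditions are stop > first dose (TEAE) and stop < first dose (not a TEAE). The start is June 2023 or 2023 only; both give the same result.

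| Stop | Partial-start row as written | Missing-start row |
|---|---|---|
| 4 June 2023 | not a TEAE | not a TEAE |
| 5 June 2023 | no class | TEAE |
| 6 June 2023 | TEAE | TEAE |

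Only equality fails. The missing-start row and Table 6-3 both put equality on the later side.

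**Partial stop.** The cell has no condition. The missing-start row tests the imputed stop against first dose.

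| Start | Stop | Latest possible stop | Dates consistent? | Partial-start row as written | Missing-start row |
|---|---|---|---|---|---|
| June 2023 | May 2023 | 31 May 2023 | no, stop precedes earliest start | TEAE | not a TEAE |
| June 2023 | June 2023 | 30 June 2023 | yes | TEAE | TEAE |
| June 2023 | 2023 | 31 Dec 2023 | yes | TEAE | TEAE |
| 2023 | May 2023 | 31 May 2023 | yes | TEAE | not a TEAE |
| 2023 | June 2023 | 30 June 2023 | yes | TEAE | TEAE |
| 2023 | 2023 | 31 Dec 2023 | yes | TEAE | TEAE |

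The fourth line is the error. The event had ended by 31 May, before the first dose on 5 June, so it neither started nor worsened after dosing. The first line is a data conflict that a query should resolve, not a fault of the rule.

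**Reach of the wrong class.** Two things must hold together:

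1. The start lacks its month. If the start month is known and the start could be on or after first dose, an earlier stop month contradicts the start.
2. The stop has month and year, and that month ends before first dose.

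**Effect of using the missing-start tests in both cells.** The stop on 5 June becomes a TEAE. The AE with start 2023 and stop May 2023 becomes not a TEAE. No other consistent case in the tables changes class.

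**The case against.** The strongest case against is that this hardly ever matters. Patients are in-house from the morning of Day -1 to Day 10 (SAP Section 3.1), and the AE listing carries date and time of onset (Section 4.13.1). A year-only start for an event within a screening window of at most four weeks would be an unusual record, and data queries (Protocol Section 10.1.7) should remove most such cases. All of this stands, and it limits the point to a wording repair.

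It may also be said that treating doubtful events as treatment-emergent is a sound conservative default. That is fair where there is doubt. A stop month that ended before first dose leaves none, and the missing-start row does test it. Nor does the row label already exclude such events: it describes the start date only, and the known-stop cell under the same label deals with earlier stops explicitly.

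For the gap, one could argue that the start is imputed to the first-dose date, which makes the event a TEAE anyway. But that imputation sits in the branch that requires a later stop, so as written it does not apply to equality.

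A reader might go further and infer that an event arising and resolving on Day 1 would be lost from the TEAE tables. The documents do not support this:

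- An event that begins in-house on Day 1 would ordinarily have a known start, and the known-start row makes it a TEAE.
- An AE with a partial start that ended on Day 1 may well have begun before admission. Calling it a TEAE is then a conservative convention, not the recovery of a lost event.
- How code would treat an unclassified event is not stated. Each AE is listed with a yes/no treatment-emergence field, so a blank would be visible. The blinded data review meeting (SAP Section 4.4.3.2) is described for deviations and analysis populations, so it is no guarantee of a catch.

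**Conclusion.** The point holds in limited form. The partial-stop cell gives a wrong class for one consistent pattern of dates, against both the definition in Section 4.13.1 and the table's own missing-start row. The known-stop cell does not misclassify; it leaves one case, a stop on the first-dose date, without a class. No other section of the SAP supplies either rule.

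The size is small. Few events are expected to be affected, possibly none. The documents do not say how often AE dates will be incomplete, so no frequency can be computed. A reader might express the stake as 1/6 = 16.7 percentage points in a dose group, or 1/8 = 12.5 points in pooled placebo (4 cohorts × 2 patients). Those figures are only the weight of any one patient in any incidence. They say nothing about this rule, and would apply only if the patient had no other event in the same table row.

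The conclusion rests on reading the cells literally and on pre-dose AEs being recorded from consent, as both documents state. It is a minor correction, worth making because it costs almost nothing and the SAP already contains the wording needed.

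**What to change.** In SAP Table 6-2, for partial start dates that could be on or after first dose:

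1. **Known-stop cell.** Make the AE a TEAE when the stop is on or after the first-dose date. The not-TEAE branch stays as it is.
2. **Partial-stop cell.** Impute the stop to the last day of the month, and to December where the month is missing. Class the AE as a TEAE if that date is on or after first dose, or if the stop year is missing. Otherwise class it as not a TEAE.
3. **Start date in the new not-TEAE branch.** Impute a missing day to the first of the month and a missing month to January, as the known-stop cell already does. Without this, the start in the example could still be set to 5 June 2023, after an imputed stop of 31 May 2023.

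The cost is two table cells and a small change to the derivation code, with no change to the protocol or to data collection. If the SAP is already final, Section 1 provides the Statistical Method Modification Form for such changes.
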